5.4.3 Multiple imputation

An additional sensitivity analysis of the primary outcome will be performed using multiple imputation which substitutes predicted values from a regression equation assuming Missing At Random. This will be carried out where AUC values are reported as missing based on the above criteria. The imputation will be carried out by the MI command in Stata ⁴. MI replaces missing values with multiple sets of simulated values to complete the data, performs standard analysis on each completed dataset, and adjusts the obtained parameter estimates for missing-data uncertainty using Rubin's rules to combine estimates ⁵.

The following procedure will be followed:

- Multiple imputation will be carried out by chained equations to impute the entire PYY AUC values, using the variables PYY AUC, treatment group, baseline value and the stratification variables.
- The MI will be set as wide
- A regression method will be used, where the registered variables will be individually adjusted for the randomisation and stratification factors (BMI and age), with 100 imputations to avoid biased estimates, seed (2259) and the force options
- MI estimate will provide the final results using the same regression model as the primary analysis and covariate adjustments.

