11.2 The Number of Participants

The power calculation is based on the primary outcome of change in appetite hormones and a standard deviation of AUC of 96.2pg/ml of total PYY based on a study looking at the influence of resistance and aerobic exercise on hunger and circulating levels of total PYY in healthy males (Broom 2009). To detect a minimum clinically significant difference of 120pg/ml in AUC of total PYY between groups, we will require 15 participants in each of the four arms with 80% power and 2-sided alpha of 1.7%. This will allow three comparisons between arms. To account for up to 20% dropout, 19 participants will be required in each arm; therefore 76 participants will be recruited in total.

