3.2.2 Full analysis data set using multiple imputation for missing data

A sensitivity analysis using multiple imputation will be used to impute missing data, to assess the robustness of the conclusions to missing data. More detail is in section 5.3.2. This population will be used for sensitivity analyses of the primary outcome. It will not be used for secondary outcomes.

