5.4.2 Additional Analysis

For a sensitivity analysis, we will also deal with missing data in the primary outcome (PYY postprandial responses at 24 weeks) by running a Generalised Estimating Equations (GEE) model with an exchangeable correlation matrix to compare groups, allowing for repeated postprandial measurements from the same individual. This method allows all individuals with at least a single measure of PYY to be included. In the GEE model with repeated PYY values at 24 weeks as the response variable, the effect of the intervention will be adjusted for the fasting value at the baseline and stratification variables (Age & BMI). Gaussian family distribution with identity link will be used for the response and robust standard errors to provide consistent parameter and standard error estimates. Post-hoc treatment effects for the mean PYY response over the pre to post-prandial assessment period will be analysed according to the same *a priori* contrasts and correction for multiple testing as those reported for the primary analysis.

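### The multiple imputation in SAP 5.4.3 repeats the complete-case result by construction when only the week-24 AUC is missing, and the GEE in 5.4.2 needs a sampling-time term and a small-sample variance correction

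*SAP*

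**What the plan says.** SAP 5.3.1 models week-24 time-averaged PYY AUC on arm, baseline PYY and the two stratification factors. SAP 5.4.1 counts an AUC as available if at least four of the seven samples are valid. SAP 3.2.1 keeps people with a missing baseline through the missing-indicator method.

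Two sensitivity analyses deal with missing primary-outcome data:

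- **Multiple imputation.** SAP 3.2.2 gives its purpose as "to assess the robustness of the conclusions to missing data", and Protocol 11.7 makes it the intention-to-treat analysis. SAP 5.4.3 says it will "impute the entire PYY AUC values, using the variables PYY AUC, treatment group, baseline value and the stratification variables", assuming missing at random, and then fit the primary model with the same adjustments.
- **GEE on the individual week-24 samples.** SAP 5.4.2 uses an exchangeable correlation and robust standard errors. Of the covariates it says "the effect of the intervention will be adjusted for the fasting value at the baseline and stratification variables". Of eligibility it says "This method allows all individuals with at least a single measure of PYY to be included". It names no term for sampling time, no small-sample correction and no reference distribution. The Holm thresholds of SAP 5.3.2 apply.

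**The concern.** A sensitivity analysis is useful only if it could have disagreed with the primary analysis. An imputation model holding just the analysis covariates brings in nothing new about people who have no week-24 AUC. The PYY AUCs at weeks 2, 6 and 12, which SAP 5.3.3 analyses anyway, do carry such information and are left out. The report could then present agreement as robustness when the method guarantees it. This matters because up to 20% dropout is planned for, and Protocol 8.10 allows withdrawal for intolerance, adverse events and non-compliance, any of which may differ by arm.

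The GEE raises two separate issues. It gives fasting and post-meal samples one common mean while admitting people with a single sample. It also relies on a large-sample variance with only 60 to 76 participants.

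**Working it through.** **Step 1. The plan's own figures.** The inputs in Protocol 11.2 are "a standard deviation of AUC of 96.2pg/ml of total PYY", a "minimum clinically significant difference of 120pg/ml in AUC of total PYY between groups", 80% power and a two-sided alpha of 1.7%.

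- n per arm = 2 × (z₀.₉₉₁₅ + z₀.₈₀)² × (96.2/120)² = 2 × (2.387 + 0.842)² × 0.643 = 13.4, so 14.
- With the t distribution, power is 76.8% at 14 and 80.3% at 15. The stated 15 is reproduced.
- The protocol continues: "To account for up to 20% dropout, 19 participants will be required in each arm". 15/0.8 = 18.75, so 19, and 4 × 19 = 76. The GEE therefore has about 60 to 76 clusters.

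**Step 2. Why the imputation repeats the complete-case estimate.** Let b be the complete-case least-squares estimate, with X_o the design rows of people with a week-24 AUC and X_m those without. Imputed values are drawn around X_m·b. The completed-data estimate is (X'X)⁻¹(X_o'y_o + X_m'y*). On average over imputations, X_o'y_o = X_o'X_o·b and X_m'y* = X_m'X_m·b. The sum is X'X·b, so the estimate is b again. This is exact for the normal model that SAP 5.3.1 expects. It needs the baseline covariate to be observed.

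**Step 3. Size by simulation.** Setting: 19 per arm, about 20% of week-24 AUCs missing, 100 imputations. Assumptions not in the documents: baseline/follow-up correlation 0.6, and dropout depending on week-12 PYY in opposite directions in two arms. Bias in the empagliflozin-placebo contrast, pg/ml:

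| Week-12/week-24 correlation (assumed) | Complete case | MI as in SAP | MI plus week-12 AUC |
|---|---|---|---|
| 0.5 | +5.9 | +5.7 | -1.8 |
| 0.7 | +13.8 | +13.8 | -3.0 |
| 0.85 | +23.9 | +23.9 | -0.4 |

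Monte Carlo error is about 1.3. Complete case and SAP MI correlate at 0.998-0.999 and differ on average by 0.04 SE, which is 0.04 × 29 ≈ 1.2 pg/ml. Mean SEs are 28.5-29.6 (complete case) and 28.7-29.9 (MI).

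A second simulation used a true difference of 60 and 22% dropout in the active arm only. At correlation 0.85 the complete-case bias was about +13. Adding interim AUCs removed it if every dropout had interim data, left about +5.5 if half had gone before week 6, and left all of it if all had. At correlation 0.5 the bias was about +4.

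**Step 4. GEE without a time term.** Setting: 15 per arm, assumed post-meal rise 50-80 pg/ml, 500 trials per pattern, Monte Carlo error about 26.6/√500 = 1.2.

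- 3 of 15 in one arm with only a fasting sample: bias -8.4, falling to +0.4 with time indicators.
- The same three people with the 0, 30 and 60 minute samples: -0.5 with or without the time term.
- Complete curves (2,000 trials): -0.1. If incomplete curves are balanced across arms, the shift is common to them and cancels from the contrast.

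**Step 5. GEE robust errors under no effect** (sandwich variance × K/(K-1), normal reference, complete curves).

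| Participants per arm | Mean SE / true SD | Type I at 1.7% | Type I at 5% | Any rejection at first Holm step |
|---|---|---|---|---|
| 15 | 25.06/26.51 = 0.945 | 3.9% | 6.9% | 8.6% |
| 19 | 22.25/24.25 = 0.918 | 3.0% | 7.7% | 7.9% |

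Two further simulations at 15 per arm gave 3.0% and 3.4% at nominal 1.7%. Ordinary regression on the AUC held its level (1.8% at 1.7%, 5.0% at 5%). Time indicators do not repair the standard errors: with 15 per arm, type I error stayed at 3.5%.

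**The case against.** A reader might infer that both sensitivity analyses fail at their task. The documents do not support that. The GEE is meant to bring in people with one to three week-24 samples, whom the four-of-seven rule excludes, and it does so. It cannot address people with no week-24 sample, but it is not offered for that.

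A reader might also infer that the imputation can never differ from the primary analysis. SAP 5.4.3 specifies chained equations and refers to registered variables in the plural. If a missing baseline AUC is imputed too, those participants are handled differently from the missing-indicator method and the results can differ. The text also does not say which visits its PYY AUC covers. If all visits were meant, much of the point falls away, but the SAP must then say so.

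The sizes depend on the chosen scenarios. Visit correlations and dropout driven by week-12 PYY are assumptions, and early dropout removes the gain. A bias of +13 is about half a standard error (27) and 13/120 = 11% of the target difference. The GEE shift needs one-sided, badly timed gaps, which nothing in the documents predicts, and 8/120 is 7% of the target. The standard-error shortfall is 5-8% and presumes a normal reference that the SAP does not state.

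It is also tempting to extend the GEE criticism to the visit-level GEE in SAP 5.3.3. That analysis is described as a summary, no robust errors are stated for it, and it was not tested here.

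All of this stands as a limit on size and scope. It does not alter Step 2.

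**Conclusion.** The point holds in a bounded form. Reading PYY AUC in SAP 5.4.3 as the week-24 value, and with baseline observed, the imputation reproduces the complete-case estimate by algebra. Agreement between the two therefore says nothing about missing data. Interim AUCs would remove roughly 4 to 24 pg/ml of bias under the assumed correlations and dropout mechanism, and less or none when dropouts leave before the interim visits.

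The GEE is useful but under-specified. Its contrast can move by about -8 pg/ml when incomplete curves are both unbalanced between arms and unrepresentative in timing, and by about 0 otherwise. Without a small-sample correction, and with a normal reference, it rejects about 3-4% of the time at nominal 1.7%.

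These are sensitivity analyses. The primary estimate, the primary test and the sample size do not change.

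**What to change.** - **SAP 5.4.3:** add PYY AUC at weeks 2, 6 and 12 to the imputation model. State which visits' AUCs are imputed and whether a missing baseline is imputed. Reconcile the first bullet, which includes baseline, with the third, which names only randomisation and stratification factors. Say in the report that this analysis still assumes missing at random and how many dropouts had interim PYY. A delta-adjusted imputation would be a separate addition if departures from that assumption are to be examined.
- **SAP 5.4.2:** add sampling time as a seven-level factor, and use a small-sample variance correction with a t reference, or replace the GEE with a mixed model using Kenward-Roger. Using baseline AUC instead of baseline fasting PYY is optional, for precision only.

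The cost is SAP wording and code. All the variables are already collected.

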11.7 Inclusion in Analysis

All analyses of outcome data will be carried out on a complete case basis according to randomised group. Therefore those with missing outcome data will be excluded from this analysis. As a sensitivity analysis, for the primary and main secondary outcome, multiple imputation will be used to perform an intention to treat analysis, and to assess the impact of missing outcome data. We will also conduct a per protocol analysis excluding those who report no longer taking their randomised treatment at the four follow ups.

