5.3 Analysis methods

5.3.1 Analysis of primary and secondary outcomes

A generalised linear model will be used with PYY 3-hour time averaged AUC at 24 weeks entered as the dependant variable and randomisation group entered as a categorical independent variable with the placebo control group as the reference. The effect of the intervention will be adjusted for baseline value of PYY and stratification variables (Age & BMI grouped as two categories as per the stratification method). Data will be checked for normality with an appropriate distribution (i.e. gamma) or transformation used if time averaged AUC PYY is not normally distributed, although we anticipate data will be normally distributed. The overall p value for the effect of treatment will be reported.

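### As most naturally read, the multiple imputation in SAP 5.4.3 uses only the primary model's own covariates, so it returns the complete-case estimate and cannot test robustness to dropout at week 24

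*SAP*

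**What the plan says.** The main analysis is complete case (SAP 3.2.1). Its model regresses week-24 time-averaged PYY AUC on randomised arm, and "The effect of the intervention will be adjusted for baseline value of PYY and stratification variables", meaning the age and BMI categories (SAP 5.3.1).

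Multiple imputation is a sensitivity analysis of the primary outcome. SAP 3.2.2 gives its purpose as "to assess the robustness of the conclusions to missing data". Protocol 11.7 goes further: "multiple imputation will be used to perform an intention to treat analysis, and to assess the impact of missing outcome data".

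SAP 5.4.3 describes a method that "substitutes predicted values from a regression equation assuming Missing At Random". The AUC is imputed whole, by chained equations, "using the variables PYY AUC, treatment group, baseline value and the stratification variables". The third bullet describes the regression again and does not repeat the baseline value: "the registered variables will be individually adjusted for the randomisation and stratification factors (BMI and age"). It also sets the number of imputations at 100. Finally, "MI estimate will provide the final results using the same regression model as the primary analysis and covariate adjustments".

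PYY AUC is also obtained at weeks 2, 6 and 12 (SAP 5.1). Section 5.4.3 does not name these values, and no analysis under a missing-not-at-random assumption is planned.

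**The concern.** The imputation model and the analysis model appear to hold the same terms. If so, an imputed participant adds no information. The analysis makes the same missing-data assumption as complete case and gives the same answer, whether or not dropout has distorted that answer. Readers would take the agreement as evidence that dropout did no harm.

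This matters because withdrawal can be related to treatment. Participants who do not tolerate the study drug leave the study (Protocol 8.10 and 9.1), as do those who need an excluded medication (Protocol 9.5). The last interval, weeks 12 to 24, is the longest, so some who leave may already have given follow-up PYY values that 5.4.3 does not use. The documents do not say when dropout is expected.

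**Working it through.** **1. The plan's own figures.** Inputs from Protocol 11.2 and SAP 2.3: SD 96.2 pg/ml, difference 120 pg/ml, two-sided alpha 1.7%, power 80%, dropout 20%. The normal approximation gives 2 × (2.387 + 0.842)² × (96.2/120)² = 13.4, so 14 per arm. The noncentral t gives 80.3% power at 15 per arm, which reproduces the plan. Then 15/0.8 = 18.75, so 19 per arm and 4 × 19 = 76. About 4 of 19 per arm would lack week 24, leaving about 60 observed outcomes.

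**2. Why the two estimates coincide.** Let X hold arm, baseline and strata, with rows split into observed (o) and missing (m). The complete-case estimate is b = (Xo′Xo)⁻¹Xo′yo. Averaged over many imputations from the same X, the imputed outcomes are Xm b. Refitting on everyone gives

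(Xo′Xo + Xm′Xm)⁻¹(Xo′yo + Xm′Xm b) = (Xo′Xo + Xm′Xm)⁻¹(Xo′Xo + Xm′Xm) b = b.

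Only the noise from a finite number of imputations remains. With a complete-case SE of 28.96 (step 3, setting B), the variance is 839. With 19 rather than 15.2 per arm it would be 839 × 15.2/19 = 671, so the between-imputation variance is about 168. Over 100 imputations the noise SD is √(168/100) = 1.30 pg/ml, and its mean absolute size is 1.30 × √(2/π) = 1.0 pg/ml.

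**3. Simulation check.** Common inputs: 19 per arm, SD 96.2, no true effect, 100 imputations, Rubin's rules, complete baselines. The between-visit correlations and dropout mechanisms are assumptions; the documents give none.

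- Setting A: 4 per arm missing, visit correlation 0.5, 0.7 or 0.85, 1,500 trials each. Correlation of the two estimates 0.999, mean absolute difference about 1 pg/ml, SE 25.9 (imputation) against 25.7 (complete case) at correlation 0.7.
- Setting B: 20% missing at random, baseline-to-follow-up correlation 0.6, week-12-to-24 correlation 0.8, 2,000 trials. Correlation 0.9988, mean absolute difference 1.1 pg/ml, SE 29.2 against 29.0. At 10% and 30% dropout the correlation is 0.9994 and 0.9980. At 20% it stays 0.9988 for baseline correlations from 0.3 to 0.8.

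**4. Bias (pg/ml, true effect zero).** Setting A adds the AUCs at weeks 2, 6 and 12; setting B adds week 12 only.

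| Dropout depends on | Complete case | As in 5.4.3 | Earlier AUCs added |
|---|---|---|---|
| Week-12 PYY, one arm (A; correlation 0.5 / 0.7 / 0.85) | 8.4 / 6.8 / 4.0 | 8.4 / 6.9 / 4.0 | 0.7 / 0.7 / 0.1 |
| Week-12 PYY, all active arms (B) | 14.01 | 14.02 | 0.70 |
| Unseen week-24 PYY, one arm (correlations as in A) | 18.7 / 13.8 / 6.5 | as complete case (step 2) | 15.2 / 10.4 / 4.2 |
| Unseen week-24 PYY, all active arms (B) | 19.63 | 19.65 | 11.02 |

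A further run with week-12-dependent dropout gave about 3–9 pg/ml falling to about 0–2. In rows 3 and 4 the share of bias removed is 3.5/18.7 = 19%, 3.4/13.8 = 25%, 2.3/6.5 = 35% and 8.61/19.63 = 44%.

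**5. Precision under random dropout (A).** With the earlier AUCs the empirical SE falls from 31.8 to 31.2, 26.2 to 25.4 and 18.0 to 17.4, that is by 1.9%, 3.1% and 3.3%. In B it falls from 28.65 to 27.50, or 4.0%.

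**6. Where the 0.999 does not hold.** SAP 3.2.1 handles missing baselines by a missing indicator, whereas the imputation would fill them in. With 3% or 5% of baselines missing, the correlation is 0.992 or 0.988. If bullet 3 is taken literally and baseline is left out of the imputation, it is 0.916 (mean absolute difference 9.1 pg/ml). Neither difference says anything about dropout. The first reflects baseline handling; the second arises because imputed values ignore a covariate of the analysis model.

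**The case against.** The strongest reply is that the text can be read otherwise. Chained equations are needed only when several variables are incomplete, and the section speaks of registered variables in the plural. If the AUCs from every visit were registered, each could help predict the others. So a reader might infer that the SAP rules the earlier visits out, and the wording does not go that far. It does not bring them in either: no earlier visit is named and the section concerns the week-24 outcome, so week 24 with baseline is the more natural reading. Likewise, bullet 3 may simply list the complete predictors in the chain, with baseline entering through the chain. Both ambiguities need the same edit.

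A reader might also infer that participants with one to three valid week-24 samples are lost to every analysis. They are not: the GEE in SAP 5.4.2 keeps anyone with at least one week-24 value. But it keeps no one without a week-24 visit. The GEE in SAP 5.3.3 and the multilevel models in Protocol 11.1 use the earlier visits, but address the response over time, not the week-24 effect.

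Two further objections stand in part. Dropout driven by week-12 PYY favours a remedy that adds week-12 PYY, and the documents do not establish that mechanism. The biases are also modest: 4.0 to 8.4 pg/ml is 3% to 7% of 120 and about a quarter of an SE (8.4/31.8 = 0.26); 14.0/29.0 is about half an SE. These limit the size of the problem. They do not restore the analysis as a robustness check.

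**Conclusion.** The point holds on the most natural reading of SAP 5.4.3. With complete baselines and the linear model that the SAP expects to use, the imputed result equals the complete-case result apart from about 1 pg/ml of noise. It therefore carries the same bias and cannot assess the impact of missing week-24 outcomes. The algebra needs no assumption about the dropout mechanism. The bias figures do rest on assumed mechanisms and correlations.

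Three stronger conclusions are not supported. The 0.999 is a conditional simulation result, not a figure from the documents. Nothing here shows that dropout has biased, or will bias, the primary result. And adding the earlier visits does not settle the matter, because if dropout depends on the unseen week-24 value, 56% to 81% of the bias remains in these simulations. Since this is a sensitivity analysis, the change should be made, but it does not alter the main inference.

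**What to change.** In SAP 5.4.3:

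1. Name PYY AUC at weeks 2, 6 and 12 as variables in the chained-equation model, together with week-24 AUC, arm, baseline AUC and the age and BMI strata.
2. Reconcile bullet 3 with bullet 1, so that baseline and the earlier AUCs are plainly predictors of week-24 AUC.
3. Leave the analysis model unchanged.
4. Add a delta-shift run in which the imputed active-arm values are moved by fixed steps, for example up to 120 pg/ml, and report where the conclusion changes. Only this step addresses dropout that depends directly on the unseen value.

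The cost is SAP wording and a few lines of code, and all the variables are already collected. The imputation regression grows from 7 coefficients (intercept, three arm terms, baseline, two strata) to 10, on about 60 observed outcomes. Participants who left before week 2 gain nothing from the first step. Body weight as a further predictor, and imputation at the level of single samples, are optional; neither was tested here.

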5.4.4 Per-protocol

The primary outcome analysis will be repeated when restricted to a per-protocol dataset (see Section 3.2.3)

5.4.5 Subgroup analyses for primary outcome

No subgroup analyses are planned.

5.5 Safety data

The number (%) of individuals experiencing either an adverse event or a serious adverse event will be summarised by randomised group.

